### **8.1.2. Evaluating and Recording of Adverse Events**

At each visit all AEs that occur from the time of treatment and throughout a patient’s study participation that are observed, elicited by the site personnel, or reported by the patient, will be recorded in the source documentation and appropriate section of the AE eCRF and evaluated by an assessor.

Minimum information required for each AE includes type of event, duration (start and end dates), severity, seriousness, causality to investigational medicinal product, action taken, and outcome.

Severity of AEs will be graded by the Principal Investigator using the Common Terminology Criteria for AEs (CTCAE) version 4.0 (refer to the Study Manual or [http://ctep.cancer.gov/protocolDevelopment/electronic\\_applications/ctc.htm](http://ctep.cancer.gov/protocolDevelopment/electronic_applications/ctc.htm)).

For AEs not listed in the CTCAE, the following definitions should be used:

Grade 1	Mild Symptomatic or mild symptoms Clinical or diagnostic observations only Intervention not indicated
Grade 2	Moderate Minimal, local or noninvasive intervention indicated Limiting age-appropriate instrumental activities of daily living (ADL)*
Grade 3	Severe or medically significant but not immediately life-threatening Hospitalization or prolongation of hospitalization indicated Disabling Limiting self care ADL**
Grade 4	Life-threatening consequences Urgent intervention indicated
Grade 5	Death related to AE

\*Instrumental ADL refer to preparing meals, shopping for groceries or clothes, using the telephone, managing money, etc.

\*\*Self care ADL refer to bathing, dressing and undressing, feeding self, using the toilet, taking medications, and not bedridden.

The relationship of the AE to the investigational medicinal product should be specified by the Principal Investigator, using the following definitions:

1. Not Related: Concomitant illness, accident or event with no reasonable association with treatment.
2. Unlikely: The reaction has little or no temporal sequence from administration of the investigational medicinal product, and/or a more likely alternative etiology exists.

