#### **8.1.5. Clinical Management of Index Knee-related Events**

In the event that the patient has an immediate reaction following administration of study medication or returns to the clinic with an acute exacerbation (e.g., tenderness, increased pain, swelling, effusion, decreased mobility of the index knee), the patient should be treated according to local clinical guidelines and physician experience.

If the index knee is aspirated at any time after administration of study medication for any reason, the volume of synovial fluid aspirated must be documented, synovial fluid should be (1) cultured, (2) evaluated for presence of crystals, and (3) assessed for white cell count at a local laboratory, and the results should be documented.

Any event that is a change from the patient's baseline status (new or worsening case) should be reported as an AE and those meeting the definition of serious must be reported in accordance with Section 8.1.3.

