#### **9.4.4. Safety Analyses**

AEs will be coded using the Medical Dictionary for Regulatory Activities (MedDRA) dictionary. Incidences (number and percent) TEAEs, those events that started after dosing or worsened in severity after dosing, will be presented by treatment group. Incidences of TEAEs will also be presented by maximum severity and relationship to study medication. Similar presentations will be provided for serious AEs, AEs leading to withdrawal from the study, or AEs leading to death.

Analysis of AE data will include examination of the incidence rates and changes in severity of TEAEs and index knee related TEAEs following the first dose and second dose, as well as the cumulative incidence of TEAEs after all doses of FX006. Both the number of events and the number of patients experiencing an event will be examined to assess the by patient cumulative incidence of TEAEs associated with repeat administration. The cumulative TEAE incidence rate will also be compared with total exposure to FX006.

Clinical laboratory data and vital sign information will be presented as descriptive summary statistics for value and change from Baseline at each individual time point.

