#### 4.10.1. Adverse Events

Adverse events will be coded using the MedDRA (version 19.1) coding system and displayed in tables and data listings using system organ class (SOC) and preferred term (PT).

Analyses of AEs will be performed for those events that are considered treatment-emergent, where treatment-emergent is defined as any AE with onset after the administration of study treatment, or any event that was present at baseline but worsened in intensity through the end of the study.

If the start date/time of an AE is partially or completely missing, the date/time will be compared as far as possible with the date/time of the start of administration of study drug. The AE will be assumed to be treatment emergent if it cannot be definitively shown that the AE did not occur or worsen during the treatment-emergent period (worst case approach). The following general rules will be used:

- If the start time of an AE is missing but the start date is complete, an AE will only be excluded as being treatment emergent if the start date is before the date of study drug administration or if the stop date/time is before study drug administration.
- If the start time and day are missing but the start month and year are complete, an AE will only be excluded as being treatment emergent if the start month/year is before the month/year of study drug administration or if the stop date/time is before study drug administration.
- If the start day and month are missing but the start year is complete, an AE will only be excluded as being treatment emergent if start year is before the year of study drug administration or if the stop date/time is before study drug administration.
- If the start date is completely missing, an AE will be considered treatment-emergent unless the stop date/time is before study drug administration.

Adverse events will be summarized by patient incidence rates; therefore, in any tabulation, a patient contributes only once to the count for a given SOC or preferred term.

Summary tables will display the number and percentage of patients who experienced at least one TEAE in each of the following categories:

- Any TEAE
- Any Serious Adverse Event (SAE)
- Any TEAE leading to study discontinuation
- Any TEAE by severity (grade 1-5)
- Any TEAE by relationship
- Any index-knee related TEAE
- Any index-knee related SAE
- Any index-knee related TEAE leading to study discontinuation

- Any index-knee related TEAE by severity (grade 1-5)

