- Any index-knee related TEAE by relationship
- Any TEAE related to injection procedure

Separate tabulations will be produced for each of following categories:

- All TEAEs by SOC and PT
- All SAEs by SOC and PT
- All TEAEs related to study drug by SOC and PT
- All TEAEs related to injection procedure by SOC and PT
- All TEAEs by maximum severity by SOC and PT
- All TEAEs leading to study discontinuation
- All TEAEs leading to death
- All index-knee related TEAEs by SOC and PT
- All index-knee related TEAEs related to study drug by SOC and PT
- All index-knee related TEAEs by maximum severity by SOC and PT

Summary tables and the tabulation of All TEAEs by SOC and PT will be presented for the following patient groups and time periods, with a separate table for each patient group:

1. Patients receiving only one dose
  - a. First dose to Week 12
  - b. First dose to Week 24 (end of study)
2. Patients receiving the second dose at Week 12
  - a. First dose to Week 12
  - b. Week 12 to Week 24
  - c. Week 12 to Week 52
3. Patients receiving the second dose at Week 16
  - a. First dose to Week 16
  - b. Week 16 to Week 32
  - c. Week 16 to Week 52
4. Patients receiving the second dose at Week 20
  - a. First dose to Week 20
  - b. Week 20 to Week 40
  - c. Week 20 to Week 52
5. Patients receiving the second dose at Week 24
  - a. First dose to Week 24
  - b. Week 24 to Week 48
  - c. Week 24 to Week 52

Summary tables and all tabulations will be presented for the following time periods for patients receiving two doses only (same table):

1. Baseline to Week 52
2. Baseline to Week 12
3. Second dose to 12 weeks after second dose

Date and time of onset of TEAE will be used to assign the time periods.

In the summary table for "Any TEAE by SOC and PT", an additional row with the number of events observed will be presented. A patient will be counted once for the number of patients if they have multiple events. The total number of events will be the absolute number of events observed, and a patient will be counted more than once for the event totals if they have multiple events.

In these tabulations, related is defined as any TEAE deemed possibly, probably or definitely related to study drug by the investigator. If relationship is missing, it will be imputed as related.

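### SAP 4.10.1 places TEAEs in dose periods by onset alone, so worsening after dose 2 of an AE that began after dose 1 may be missing from the second-dose columns

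*SAP*

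**What the plan says.** **Protocol 9.4.4.** TEAEs are "those events that started after dosing or worsened in severity after dosing". The section also promises to examine "incidence rates and changes in severity of TEAEs and index knee related TEAEs following the first dose and second dose".

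**SAP 4.10.1, definition.** An AE is treatment-emergent if its onset follows study treatment. The only worsening limb is "any event that was present at baseline but worsened in intensity through the end of the study". SAP 4.2.10 defines a separate baseline for the second dose, but the AE section does not use it.

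**SAP 4.10.1, allocation.** "Date and time of onset of TEAE will be used to assign the time periods". This governs two sets of tables:
- By-group tables, one per second-dose timing (Weeks 12, 16, 20, 24), each with a first-dose column and two second-dose columns.
- A pooled two-dose table with columns for baseline to Week 52, baseline to Week 12, and "Second dose to 12 weeks after second dose".

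**Grade.** The by-group summaries include rows by severity grade. The pooled set adds "All TEAEs by maximum severity by SOC and PT". Neither states whether the grade is the one reached within the column's period or over the whole event.

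**Recording.** Protocol 8.1.2: "Minimum information required for each AE includes type of event, duration (start and end dates), severity, seriousness". The list that follows contains no date of grade change. For index-knee events, Protocol 8.1.5 says: "Any event that is a change from the patient's baseline status (new or worsening case) should be reported as an AE".

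**The concern.** The primary objective is the safety and tolerability of repeat administration. The first-dose and second-dose columns are the main display bearing on it. Aggravation of an existing knee problem by a second injection is one of the harms a repeat-dose study should be able to show.

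Such cases are plausible. The repeat-administration criteria bar patients with major safety concerns after dose 1, but they do not bar those with an ongoing mild or moderate AE. An AE that starts after dose 1 is already a TEAE by onset. If it later worsens, the SAP gives that worsening no date and no route into a second-dose column. Where the gap operates, it always lowers the second-dose count.

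**Working it through.** The documents give no figure for this point, so the check has two parts: where the rule puts a test event, and how many such events there might be.

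**1. Placement of a test event**

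The event begins after dose 1 and worsens three weeks after dose 2. Onset is set either at Week 8 or two weeks before dose 2. The period limits are those listed in SAP 4.10.1.

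*If the AE is kept as one record with its one onset date:*

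| Second dose | Onset | By-group, first-dose column | By-group, second-dose columns | Pooled, baseline to Week 12 | Pooled, 12 weeks from dose 2 | Pooled, baseline to Week 52 |
|---|---|---|---|---|---|---|
| Week 12 | Week 8 or 10 | yes | no | yes | no | yes |
| Week 16, 20 or 24 | Week 8 | yes | no | yes | no | yes |
| Week 16, 20 or 24 | Week 14, 18 or 22 | yes | no | no | no | yes |

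The second-dose columns are empty in every row. In the last row the event is in neither per-dose column of the pooled table.

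*If the worsening is entered as a new AE with its own onset:* the initial record stays where the table shows it. The worsened record falls in both by-group second-dose columns and in the pooled second-dose column, for all four timings. Nothing is lost.

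The result therefore turns on the recording convention, which neither document states.

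**2. Illustrative size, one term only**

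Share of two-dose patients affected = a × o × w, where:
- a = proportion with arthralgia after one dose. Protocol 5.2.8 gives 9.8%; its counts reproduce this (67/687 = 9.75%). It covers any joint and any FX006 dose.
- o = proportion of those events ongoing at dose 2. **Assumed** 10% to 50%.
- w = proportion of ongoing events that worsen after dose 2. **Assumed** 10% to 50%.

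Low: 0.098 × 0.10 × 0.10 = 0.00098, about 0.1 per 100.
High: 0.098 × 0.50 × 0.50 = 0.0245, about 2.5 per 100.

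In patients:
- About 180 two-dose patients (0.90 × 200, taking the share above 90% in SAP section 5 and the planned enrolment of about 200): 180 × 0.00098 = 0.2 to 180 × 0.0245 = 4.4.
- The planning figure of 132 (0.66 × 200): 0.1 to 3.2.

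**3. Protocol against SAP**

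The protocol's worsening limb refers to dosing in general. The SAP narrows it to events present at baseline. The SAP contains no analysis of change in severity by dose. SAP section 5 lists two changes, the dropped one-dose versus two-dose comparisons and the replaced time-to-maximal-relief analysis, and does not mention this one.

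**The case against.** The strongest reply is that nothing need be lost. Protocol 8.1.1 makes clinically significant worsening of a preexisting condition an AE, and 8.1.5 does the same for index-knee events. A site following these could open a new record after dose 2, and the onset rule would then place it correctly. One could also read onset of a TEAE as the date it became treatment-emergent, since otherwise events present at baseline that worsened would fit no period. Both readings are possible and neither is stated. Protocol 8.1.5 compares with the patient's baseline, not with status at dose 2, and Protocol 8.1.4 has AEs followed to resolution or a stable outcome, which fits a single record. With about 20 centers, an unstated convention leaves the count to site habit.

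Other points stand in part:
- The events are not invisible. They remain in the baseline-to-Week-52 column; SAEs and discontinuations are listed by patient; dated listings carry the study day relative to dose 2; index-knee inflammation is summarised at the second-dose and final visits. None of these gives a second-dose TEAE incidence.
- The synopsis omits the words on changes in severity that Protocol 9.4.4 contains. The synopsis does, however, count worsening after dosing as treatment-emergent.

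A reader might infer more than the documents support:
- *That dose 1 incidence is inflated.* It is not. The event did begin after dose 1 and belongs there. Only its grade could be overstated.
- *That the event is always shown at its final grade.* This is an inference from the single severity item listed and an undefined maximum.
- *That the event is always charged to dose 1.* The last row of the table above shows otherwise for the pooled display.
- *That a between-dose severity comparison would reverse.* The size estimate covers any grade rise, not Grade 3, and no calculation shows a reversal.

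**Conclusion.** The point holds conditionally. SAP 4.10.1 allocates by onset and has no rule for worsening after dose 2 of an AE that began after dose 1. If such an AE is kept as one record, its worsening is absent from every second-dose column, and the first-dose grade may be overstated. If sites open a new record, the problem does not arise. Independently of that convention, the SAP departs from Protocol 9.4.4 without listing the departure in section 5.

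The size is unknown. The range of about 0.1 to 2.5 per 100 two-dose patients rests on assumed proportions ongoing and worsening, and on an arthralgia rate not specific to the index knee. It is small, but it concerns the primary objective and the error in the second-dose count runs in one direction. The change should be made.

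**What to change.** In SAP 4.10.1, for two-dose patients:

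1. Define second-dose emergence against status just before dose 2. An AE ongoing at dose 2 that then rises in CTCAE grade or becomes serious also counts in the second-dose period, at the grade reached there.
2. Use the maximum grade reached within each period in every severity row and table.
3. Add the summary of changes in severity by dose from Protocol 9.4.4, or list its removal in SAP section 5.
4. State how worsening of an open AE is recorded in the eCRF.

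SAP section 5 shows that most second doses had already been given when it was written, so a new recording instruction would come too late for many patients. Recover worsening dates by queries limited to AEs ongoing at dose 2. Where a date cannot be recovered, show a separate row for events ongoing at the second dose, with their final grade.

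The cost is SAP and eCRF-guideline wording and a few targeted queries. Some events will appear in both period columns, which needs a footnote, and the second-dose figures may look slightly less favourable.

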#### **4.10.2. Laboratory Data**

Clinical laboratory values will be expressed in the international system of units (SI).

The following values will be summarized for each hematology and clinical chemistry laboratory parameter for all patients combined:

1. Baseline (Screening) - Observed
2. Second dose visit (two-dose group only) - Observed and change from baseline
3. Final study visit - Observed and change from baseline

In the event of repeat values, the last non-missing value per study visit will be used.

All laboratory data, including Common Terminology Criteria for Adverse Events (CTCAE) 4.03 grade, will be provided in data listings. See [Appendix A](#) for CTCAE grade definitions.

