**4.2.10.      Baseline Definitions**

Baseline for the first dose is the baseline/Day 1 assessment prior to administration of the first dose of study treatment. If the baseline result is missing, the last non-missing result prior to administration of study treatment may be used from the Screening period.

Baseline for the second dose of study treatment is defined as the last data collected prior to the second dose of study treatment administration. This is the same study visit, as long as the data are collected prior to the second dose.

Where noted in this SAP, change from baseline for efficacy analyses are also performed where baseline for the second dose is defined as the baseline/Day 1 assessment prior to administration of the first dose of study treatment.

Additional baselines may be defined to explore efficacy endpoints comparing the first dose and the second dose of study treatment administration. All new baseline definitions will be fully specified and documented in an interim SAP (iSAP) and in the final CSR.

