### 4.10. Safety Analyses

Safety analyses will be conducted using the SP. All change from baseline values will be calculated based on the pre-dose (screening) value.

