#### **4.10.3. Vital Signs, Physical Examination, and Index Knee Assessment**

The following values will be summarized for each vital sign parameter for all patients combined:

1. Baseline - Observed
2. Second dose visit (two-dose group only) - Observed and change from baseline
3. Final study visit - Observed and change from baseline

In the event of repeat values, the last non-missing value per study visit will be used.

Vital sign measurements will be presented for each patient in a data listing.

All clinically significant abnormalities noted in the physical examination will be presented in a data listing.

The following values will be summarized for incidence of inflammation, as determined from the index knee assessment, for all patient combined:

1. Baseline - Observed
2. Second dose visit (two-dose group only) - Observed
3. Final study visit - Observed

For those patients experiencing inflammation, the details of the inflammation (tenderness, swelling, effusion, heat/redness, Baker's cyst) will also be presented. In these tabulations, percentages will be based on those patients who have a non-missing index knee assessment at a given visit.

Index knee assessment as well as index knee aspiration data will be presented in a data listing.

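### Laboratory and vital-sign tables merge final visits taken at different times and show no change after the second dose

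*SAP*

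**What the plan says.** SAP 4.10.2 introduces the laboratory table with "The following values will be summarized for each hematology and clinical chemistry laboratory parameter for all patients combined". It has three entries: the screening value, then "Second dose visit (two-dose group only) - Observed and change from baseline", then "Final study visit - Observed and change from baseline". SAP 4.10.3 sets up vital signs in the same way ("The following values will be summarized for each vital sign parameter for all patients combined") with the same three visits. The index-knee inflammation table in that section also pools all patients at these three visits, but gives observed incidence only.

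SAP 4.10 fixes the reference point for every safety table: "All change from baseline values will be calculated based on the pre-dose (screening) value". SAP 4.2.10 does define another one: "Baseline for the second dose of study treatment is defined as the last data collected prior to the second dose of study treatment administration". The WOMAC analyses in SAP 4.9.1.2 use it; the laboratory and vital-sign sections do not.

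Protocol 9.4.4 plans laboratory and vital-sign summaries "for value and change from Baseline at each individual time point". SAP Section 5 lists the changes from the protocol and does not mention this one.

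The final visit depends on the patient's path (SAP 2.1). It is Week 12 for patients without benefit, Week 24 for those never eligible for a second dose, and Week 52 for two-dose patients whenever that dose was given. Protocol 7.4.4 has early termination visits follow the Week 52 schedule, so they yield the same measurements at whatever time the patient leaves. Under footnote 6 to Protocol Table 1, laboratory tests and vital signs at the second-dose visit are done before dosing.

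**The concern.** The primary objective is the overall safety and general tolerability of repeat administration, meaning two doses. Laboratory values and vital signs are named safety variables (SAP 2.5.1). Their only planned aggregate summaries are the three rows above, and two features weaken them.

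First, the final row is not one time point. It places values taken 12 or 24 weeks after a single dose beside values taken 28 to 40 weeks after a second dose, and adds early terminations at any interval.

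Second, the second-dose row precedes dose 2, so its change describes the first dose only. The final row spans both doses. A shift before dose 2 and an opposite shift after it would cancel in the final row, and nothing in the tables would summarise the change after dose 2 directly.

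Other safety tables are built for the objective. Adverse events are split by number of doses, timing of dose 2 and period after dose 2 (SAP 4.10.1). X-ray tables cover two-dose patients by timing of dose 2 (SAP 4.10.5).

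**Working it through.** **1. The plan's own figure.** SAP 4.1 gives about 200 enrolled, 66% eligible for dose 2 and 75% of those completing Week 52. 200 × 0.66 = 132 and 132 × 0.75 = 99, which agrees with the stated target of about 100.

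**2. Time from dose 2 to Week 52.**

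| Dose 2 at | Weeks from dose 2 to Week 52 |
|---|---|
| Week 12 | 52 − 12 = 40 |
| Week 16 | 52 − 16 = 36 |
| Week 20 | 52 − 20 = 32 |
| Week 24 | 52 − 24 = 28 |

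SAP 1.1 says FX006 is intended to deliver drug for about 3 months. Completers' final values therefore come well after that period. Patients who stop soon after dose 2 may supply the only scheduled final values within it, and the planned row merges them with the rest.

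**3. Share of final values not from Week 52.** SAP Section 5 reports over 90% uptake of dose 2 and about 10 one-dose patients. Assume 200 enrolled and keep the plan's 25% non-completion after dose 2.

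- Two-dose patients: 200 − 10 = 190
- Non-completers after dose 2: 190 × 0.25 = 47.5, about 48
- Not from Week 52: 10 + 48 = 58, and 58 / 200 = 29%

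This is an upper bound on these assumptions, because Protocol 7.4.4 asks sites only to attempt the termination assessments. If none of the 48 attended, the share would be 10 / (200 − 48) = 10 / 152, about 7%.

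Planning rates alone give 200 − 99 = 101, about 51%, but Section 5 shows that the 66% uptake did not hold. The 33 non-completers implied by planning (132 − 99) should not be added to the 10 observed one-dose patients, since the two figures rest on different uptake.

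**4. Effect of pooling by number of doses.** Let p be the one-dose share, c the mean change to dose 2, d the mean change after dose 2, and c₁ the change in one-dose patients. The pooled final change is (1 − p)(c + d) + p·c₁. With assumed values c = 0, d = +5 and c₁ = 0:

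- p = 5%: 0.95 × 5 = 4.75
- p = 10%: 0.90 × 5 = 4.5
- p = 34% (planning): 0.66 × 5 = 3.3

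At the observed uptake the distortion is small.

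**5. Effect of the missing second baseline.** With assumed c = −5, d = +5 and c₁ = 0, the final row shows (1 − p) × 0 = 0 for any p, although the change after dose 2 is +5.

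**6. Can it be rebuilt from the planned rows?** Subtracting the second-dose row from the final row approximates the mean change after dose 2, but over different sets of patients. The spread cannot be recovered. If both change scores have SD 10 (assumed) and correlation ρ, the SD of the change after dose 2 is √(100 + 100 − 200ρ). That is 12.6, 10.0 or 6.3 for ρ = 0.2, 0.5 or 0.8, and ρ is not reported.

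**The case against.** The best case for the plan is this. The objective is the safety of two doses overall, not of the second dose alone, and change from the pre-treatment value to the end of study is a direct cumulative summary of two doses. The schedule places post-treatment laboratory tests and vital signs only at the second-dose and final visits, and both have a row. Clinically significant abnormalities are adverse events, whose tables are split around dose 2. All laboratory values (with CTCAE grade) and all vital signs are listed, with study day relative to dose 2. Section 5 dropped one-dose versus two-dose comparisons because so few patients had one dose.

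Most of this stands, and it limits the point. The planned change from the first baseline is right to keep. What it does not answer is that the final row mixes times, which the protocol's wording does not provide for, and that listings and adverse events do not summarise continuous values after dose 2. Displaying one-dose patients apart is not a comparison, so Section 5 does not stand in the way.

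A reader might go further in three ways that the documents do not support:

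- That the SAP breaks a protocol promise to show change from dose 2. Protocol 9.4.4 speaks only of change from Baseline, so that part is a gap against the objective. Only the merging of final visits departs from the protocol.
- That the safety tables as a whole ignore the second dose. The adverse event and X-ray tables do not.
- That a second-dose baseline would isolate the effect of repeat administration. The study has one arm, and no laboratory test or vital sign is scheduled between the second-dose visit and Week 52, so early effects of dose 2 would stay unseen.

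**Conclusion.** The point holds as a tabulation gap that should be closed. No planned laboratory or vital-sign table describes change after the second dose, and the single final-visit row merges Week 12, Week 24, Week 52 and early-termination values without being declared as a change from the protocol. Up to about 29% of final values would not be from Week 52. That rests on 200 enrolled, about 10 one-dose patients, 25% non-completion after dose 2 and every non-completer attending a termination visit; the true share is probably lower.

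The one-dose patients (10 / 200 = 5%) are the least of it. Mixed timing and the missing change after dose 2 carry the weight. The adverse event and X-ray analyses are not affected.

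**What to change.** In SAP 4.10.2 and 4.10.3:

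- Keep the planned change from the first baseline.
- For two-dose patients, replace the pooled final-visit row with two rows, Week 52 and early termination. In each, give the observed value, the change from the first baseline and the change from the second-dose-visit value. Early terminations before dose 2 belong with the one-dose patients.
- Keep one-dose patients' final values out of these rows. One small column, or the listing, is enough for about 10 patients.
- Show the index-knee inflammation table with the same split of visits.
- Label the added figures as change after the second dose, and note that for completers they are taken 28 to 40 weeks after it in a single-arm study.
- Record the departure from the protocol's time-point summaries in SAP Section 5 if any pooled final-visit row is kept.

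No new data are needed, because the measurements are already scheduled before dose 2 and at the final visit. The cost is a few extra table rows and some small cells, mainly for early terminations.
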